STUDY PROTOCOL

**Prospective Randomized Comparison of Efficacy and Safety in Pacemaker and Defibrillator Implantation
Via Cephalic Versus Axillary Vein Access.
The CEPHAX Study.**

Last Update Data: October 1, 2018.

INDEX

- 1) Overview.**
- 2) Introduction.**
- 3) Justification.**
- 4) Hypothesis.**
- 5) Main objective.**
- 6) Secondary objectives.**
- 7) Methodology.**
- 8) Phases of the project and Plan of work.**
- 9) Sources of information and data analysis.**
- 10) Ethical aspects.**
- 11) Bibliography.**

1) Overview.

Cardiac implantable electronic devices (CIED), a term that includes pacemakers and cardiac defibrillators, are essential therapeutic tools for the management of arrhythmias in different clinical contexts. A fundamental step in the procedure of implant of a CIED is to establish a central venous access to be able to insert one or more catheters electrodes and to place them in the cardiac chambers. The most widespread venous access technique in our midst is the subclavian pathway. However, published studies confirm the superiority of axillary and cephalic venous access in terms of efficacy and safety in the short and long term. In spite of this, there are no recommendations on the part of the scientific societies, so the choice of the access route is totally dependent on the experience and preferences of the implant physician. To date, there are no studies in our midst comparing axillary and cephalic venous accesses performed with the technique optimized by trained electrophysiologist cardiologists.

A clinical trial is designed to compare the efficacy and safety of fluoroscopy-guided axillary venous access versus improved cephalic venous access in the CIED implant. The scope of the study will be constituted by the patients who are first implanted with a CIED and the study population will be the patients who are first implanted with a CIED in the Hospital General Universitario of Ciudad Real, Spain.

2) Introduction.

Cardiac implantable electronic devices (CIED) are essential therapeutic tools for the management of arrhythmias in different clinical contexts (1, 2). Under the name of CIED are grouped pacemakers and cardiac defibrillators. Worldwide, more than 1 million implants of these devices are carried out annually (3). In Spain CIED implants are made in 230 centers, 4 most CIED are implanted in electrophysiology laboratories by electrophysiologist and the number of implants follows an increasing trend, being in the year 2015 the incidence of pacemaker first implantations/million inhabitants of 611 and that of defibrillators of 118 (5, 6).

A fundamental step in the implant procedure of a CIED is to establish a central venous access in order to insert the electrode catheters and place them in the cardiac chambers. In most procedures ($> 80\%$) it is accessed by the left axilo-subclavian axis, reserving the right side for left-handed patients or with vascular problems on the lefthand side. According to data from the European Heart Rhytm Association (7), 60% of implanters use as a preferential access vein cephalic, 20% axillary vein and 20% subclavian. In our midst, however, this proportion is quite different, with subclavian access being much more widespread.

The access route for the implant of a CIED has prognostic implications. Cephalic access has shown, in the short term, a null incidence of pneumothorax compared with the axillary or subclavian pathway, (8-10) because it does not require puncturing the subclavian region. On the other hand, in the medium and long term, when the access roads are compared, the subclavian approach has been related to a higher incidence of electrode problems as insulation defects and conductor fractures (11-13) which seems due to anatomical factors that condition the electrode's crush (14).

The technique of access through the cephalic vein for the implant of CIED has been carried out for more than five decades (15). Since it requires greater surgical dexterity, it was initially performed preferably by thoracic or cardiac surgeons. With the time, thanks to the technical improvements that have increased their percentage of effectiveness (16-22). However, the main problem for its universalization remains the

lack of knowledge of the technique on the part of many operators and an effectiveness of less than 85%.

The subclavian vein technique of access for the implant of CIED has been carried out for more than four decades without variations in it (23). It has the advantage of specifying a lower learning curve and being a fast and reliable way of access. The risk of pneumothorax, and the damage problems of the electrodes in the medium and long term, make this technique the least desirable as a way of first choice.

The technique of access through the axillary vein has been the subject of multiple improvements to become a technique that brings together advantages of the previous two (24-28). On the one hand, its speed and low incidence of complications and, on the other, its high effectiveness and capacity to accommodate a greater number of electrodes than the cephalic pathway. However, in our midst it is a technique of scant diffusion among the implanters.

There are some studies that compared the safety and efficacy of venous access techniques in the CIED implant.

Three studies have compared the axillary vein against the subclavian. The retrospective study of Sharma G et al (29), which included 478 patients undergoing a fluoroscopy-guided subclavian or axillary pacemaker implant, showed a similar efficacy of both techniques and a greater incidence of pneumothorax with the subclavian pathway. The retrospective study of Kim KH et al (30), which included 1161 patients with an average follow-up of 8 years, was able to objectively lower long-term incidence of electrode-related complications by the axillary pathway. Finally, the prospective and randomized study of Liu P et al (31) that compared the axillary pathway "optimized" against the subclavian pathway, found a 5 times greater incidence of peri-procedural complications with the second.

Two studies have compared the axillary vein against cephalic. The prospective and randomized study of Calkins H et al (32) compared the safety and efficacy of CIED implant by cephalic access to axillary access guided by venography. It found a higher percentage of success and shorter duration of the procedure by the axillary pathway and there were no differences in the rate of peri-procedural complications. The limitation of this study is that the use of an axillary venous access technique guided by venography limits its applicability and increases the possible complications of the technique. The prospective and randomized study of Squara F et al (33) compared the safety and efficacy of CIED implant by Cephalic access to axillary access guided by fluoroscopy and performed by physicians without any training in the technique. This particular study found no difference in success or complications with both techniques, although it was objective a shorter time to get venous access by axillary. Finally, the prospective observational study of Chan NY et A (113) analyzed the success rate and long-term electrode problems of the techniques of cephalic, subclavian and axillary access guided by venography. The success of cephalic access was significantly lower than the other two. After an average follow-up of 73.6 months, the problem-free survival of the electrode was significantly higher with axillary and cephalic access.

3) Justification.

The studies published so far demonstrate the superiority of the axillary and cephalic venous accesses against subclavian venous access in the CIED implant in terms of efficacy and safety. However, the most widespread venous access technique in our midst remains the subclavian pathway.

There are no recommendations from scientific societies on which access road should be the first choice, so the technique used is totally dependent on the experience and preferences of the implant physician.

To date, there are no studies comparing axillary and cephalic venous accesses performed with the most optimized technique by trained personnel.

4) Hypothesis.

- The axillary venous access pathway is superior in terms of efficacy to the cephalic access.
- The axillary venous access pathway is equal in terms of safety to the cephalic access.

5) Main objective.

To compare the efficacy and safety of fluoroscopy-guided axillary venous access to improved cephalic venous access in the cardiac stimulation device implant.

6) Secondary Objectives:

- To compare the success rate of the accesses.
- To compare the duration of access procedures.
- To compare the duration of the implant according to the access.
- To compare the proportion of peri-procedural complications of the accesses.
- To compare the proportion of electrode problems at follow-up.

7) Methodology.

Design: randomized and open clinical trial in parallel groups.

Study population: The reference population is the patients who are implanted for the first time a CIED. The target population of the study will consist of patients who were first implanted with a CIED at the General University Hospital of Ciudad Real.

Selection criteria.

-Inclusion criteria: adults patients (>18 years old) with CIED implant indication at the General University Hospital of Ciudad Real who agree to participate in the study.

-Exclusion criteria: patients with one or more of the following characteristics:

- * pre-existing ipsilateral electrode,
- * ipsilateral lymphadenectomy,
- * cardiac resynchronization therapy indication.

Sample size and sampling procedure.

It is estimated that a sample size of 240 patients is needed for the study to have a 80% statistical power, an alpha value of 0.05 and taking into account the estimated losses due to lack of monitoring and/or data.

The selection of cases that will form the sample shall be conducted by consecutive sampling of all patients who are going to implant a CIED, meet the inclusion and

exclusion criteria, and give their consent to participate in the study. The cases will be allocated to each group (axillary venous access or cephalic venous access) by a procedure of 1:1 randomization by balanced blocks. Sealed envelopes with the number assigned to each of the subjects to be included will contain a card in which the type of venous access assigned will be required.

Period and scope of recruitment.

Patient recruitment will begin in september 2017 and continue until the required sample size is reached with an estimated time limit in december 2019.

Every patient, once recruited and performed the implant of the CIED, will be followed in the same way: before the discharge hospital with review of the device, the surgical wound and the chest X-ray and, later, ambulatory controls at 3, 6, 12 and 24 months of the Device and the generator bag.

The follow-up time will end with the completion of the study, but it may be sooner if the patient dies or moves from the hospital.

Variables:

1. Independent:

Age, sex, hypertension, diabetes, dyslipidemia, obesity, type of heart disease, renal failure, COPD, CIED indication, type of implanted CIED, assigned access route, number of implanted electrodes, type of electrode implanted.

2. Dependents:

- Efficacy: success of assigned access, duration of the access technique, duration of the procedure, time of copying, cephalic canalization, axillary canalization, finally canalized route, main cause in case of failure.
- Safety: Complications of the procedure, Pneumothorax, hematoma, dislocation electrode, venous thrombosis, long-term electrode problems, insulation defect, driver's fracture, need for new electrode implant.

8) Phases of the project and Plan of work.

The research project will be carried out in the arrhythmia unit of the General University Hospital of Ciudad Real. The two investigators will be in charge of the recruitment of the patients, the implant of the CIED and the data collection. The principal investigator will be in charge of the analysis of the data. Advice and collaboration for analysis will be requested from the HGUCR Research support unit. The commencement of recruitment will be in the fourth quarter of 2017 and completion in the fourth quarter of 2019. No funding is necessary for the realization of the project.

9) Sources of information and data analysis.

The data for the study will be obtained from the patient himself (data of filiation and personal history), of the data collection sheet that will be filled during the implant and in the postoperative and the ambulatory monitoring of the device. All data will be entered in a database with SPSS software for further analysis.

The quantitative variables will be represented by means of the mean +/-standard deviation and the qualitative variables as percentages.

To evaluate the degree of adjustment to the normality of the quantitative variables will be used the test Kolmogorov-Smirnov.

The comparison between the two study groups will be done through an intention-to-treat analysis. The comparison of quantitative and qualitative variables will be carried out with the Student's t test. The comparison of quantitative and qualitative variables with the test of the U of Mann-Withney and the comparison of two Qualitative variables with the χ^2 test. A logistics linear regression analysis will be used for multivariate analysis.

A level of statistical significance shall be considered a value of $p < 0.05$.

10) Ethical aspects.

- General ethical considerations:

The study compares two techniques of venous access for the implant of CIED that are perfectly described in the literature. Given the lack of rigorously compared to each other, there are currently no recommendations from scientific societies about which should be the first choice. Therefore, the decision to make one or the other depends fundamentally on the operator's preference and experience. Therefore, the impact on this patient population and the potential benefits derived from the results of an efficacy and safety study are important.

The prospective and randomized design of the study is justified by the greater scientific and methodological rigour that it involves.

The operators that will perform the study are perfectly trained in the realization of both techniques so that randomization will not cause any harm to the patient.

The investigators undertake to follow the procedures established by the Protocol and to inform and request the consent of all the participants. The institution is committed to ensuring the maintenance of assistance to the participants. Each of the Parties mentioned shall ensure the security and confidentiality of the identity of the subjects of the investigation.

The study will be conducted in accordance with the provisions of the Helsinki declaration (64th WMA General Assembly, Fortaleza, Brazil, October 2013).

- Information to participants:

The patients will be informed by the Investigator of the characteristics of the study and the possibility of inclusion in it. The acceptance of the patient to participate will be recorded in writing in the informed consent.

The subjects will be informed about the confidentiality of their identity and the registered clinical information that can only be reviewed by the authorized personnel.

11) Bibliography.

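### Section 4 hypothesises equal safety, but section 9 plans only tests of difference at p < 0.05, so no result of the planned analysis could support that hypothesis

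*Combined protocol and SAP*

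**What the plan says.** Section 4 (Hypothesis) lists two hypotheses of different kinds. For efficacy, axillary access is expected to be superior. For safety: "The axillary venous access pathway is equal in terms of safety to the cephalic access".

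Section 5 (Main objective) covers both: "To compare the efficacy and safety of fluoroscopy-guided axillary venous access to improved cephalic venous access". Section 6 (Secondary Objectives) has two safety items, one on complications around the procedure ("To compare the proportion of peri-procedural complications of the accesses") and one on electrode problems during follow-up. The variables in section 7 (Methodology) fill this out: "Safety: Complications of the procedure, Pneumothorax, hematoma, dislocation electrode, venous thrombosis, long-term electrode problems", followed by further lead-related items.

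Section 9 (Sources of information and data analysis) supplies the methods. "The comparison between the two study groups will be done through an intention-to-treat analysis". For binary outcomes it plans "the comparison of two Qualitative variables with the χ^2 test", and then: "A logistics linear regression analysis will be used for multivariate analysis". The only decision rule is the general one: "A level of statistical significance shall be considered a value of" p < 0.05. Categorical results are to be shown as percentages, with no interval.

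Section 7 sets the sample at 240 patients, randomised 1:1, for 80% power at alpha 0.05 with an allowance for losses. It does not say which outcome or hypothesis that number serves.

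**The concern.** Superiority and equality need different evidence. A chi-square test or a regression coefficient tested at p < 0.05 takes equality as its null hypothesis. A small p-value counts against equality. A large one means only that the data did not contradict it, which is also what a trial with too few events produces. To support equality, a plan must say how large a difference would still count as equal and show that the interval for the difference lies inside that limit. This plan does neither.

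The risk is practical. Section 2 describes the complication rate with axillary access as low, and at low rates a trial of this size will usually return a non-significant result whether or not one route is riskier. Section 2 also reports that cephalic access has had no pneumothorax, in contrast to the axillary and subclavian routes, so a real safety difference is plausible on the protocol's own account. Section 10 says the results matter because no society recommends either route. A non-significant p-value read as equal safety could therefore influence practice without evidence behind it.

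**Working it through.** **The plan's own figure.** N = 240 cannot be reproduced: section 7 gives no endpoint, rates, margin, sidedness or loss percentage. It is taken as given, which is 240 / 2 = 120 per arm. A 10% loss, an assumption, leaves 120 × 0.9 = 108 per arm.

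**Rates.** None are stated. Those below are assumptions, chosen to show a range.

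**1. How often a true doubling would be non-significant.** The test is Pearson chi-square without continuity correction, two-sided 0.05. With a and b events in two arms of n, let p̄ = (a + b)/(2n). The test rejects when |a − b|/n ÷ √(p̄(1 − p̄)·2/n) > 1.96. Power is the sum of the binomial probabilities of all pairs (a, b) that reject.

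| True rates | Power, 120 per arm | Missed | Power, 108 per arm | Missed |
|---|---|---|---|---|
| 2% v 4% | 0.129 | 87% | 0.120 | 88% |
| 5% v 10% | 0.325 | 68% | 0.293 | 71% |
| 10% v 20% | 0.59 | 41% | – | – |

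**2. What a non-significant result can hide.** Take 3/120 v 9/120. Then p̄ = 12/240 = 0.05 and z = 0.05 ÷ √(0.05 × 0.95 × 2/120) = 0.05/0.0281 = 1.78, so p = 0.076. The Newcombe 95% interval for the difference is −0.8 to +11.4 points. The result is non-significant, yet an excess of 11 points is not excluded.

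**3. What identical arms would show.** Newcombe's interval combines the Wilson limits (l, u) of each arm. When both arms have the same proportion p, the half-width is √((p − l)² + (u − p)²).

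- 2/120 in each arm: Wilson limits 0.46% and 5.87%. √(1.21² + 4.21²) gives ±4.4 points.
- 6/120 in each arm: Wilson limits 2.31% and 10.48%. √(2.69² + 5.48²) gives ±6.1 points.

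**4. What margin this sample could support.** Suppose non-inferiority is declared when the upper limit of the two-sided 95% interval (axillary minus cephalic) lies below the margin. With equal true rates and 120 per arm, exact enumeration in steps of 0.05 point gives the smallest margin with at least 80% power:

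| True rate | Newcombe | Miettinen-Nurminen |
|---|---|---|
| 2% | 6.35 points (power 0.822; 0.776 one step lower) | 6.40 points (0.822) |
| 5% | 8.60 points (power 0.811; 0.790 one step lower) | 8.70 points (0.811) |

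The usual formula, n per arm = 2p(1 − p)(1.960 + 0.842)²/margin², looks kinder. At 2% and 5 points it gives 0.0392 × 7.85/0.0025 ≈ 123.1, so 124 per arm or 248 in total, and 79% power with 120 per arm. It relies on a normal approximation that is poor with two or three expected events per arm. Enumerating the simple Wald interval gives a margin of about 5.1 points at 2%, but with a one-sided error near 5% instead of 2.5%. Power should therefore be computed for the interval method actually chosen.

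**The case against.** The best defence is that *equal* is loose wording in a short, translated investigator protocol and means only that no difference is expected. Sections 5 and 6 say only that the accesses will be compared, and the chi-square test does compare them. Nowhere does the plan say that a non-significant p-value will be reported as equality. On that reading the defect is one word.

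Part of this stands. The tests do serve the objectives in sections 5 and 6, and the problem is confined to the gap between sections 4 and 9. But equal safety is one of only two listed hypotheses, set beside a superiority hypothesis, and the main objective includes safety. Even on the loose reading, the plan never says what result would support it.

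A second objection is that low rates flatter the criticism. Section 7 lists a broad set of complications, so a composite could well exceed 5%. At 10% v 20% power is 0.59 and a doubling is detected more often than missed. That is right, and it limits the word *usually* to low rates. It does not turn a test of difference into evidence of equality.

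A third is that 240 may have been sized for efficacy. It may, but that would not make a non-significant safety test informative.

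**Conclusion.** The concern holds. Followed exactly, the plan can contradict its safety hypothesis but has no way to support it. This follows from the text and depends on no assumed rate.

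The practical size does depend on assumptions, because the documents give no complication rates. With 120 per arm, a doubling of risk goes undetected in 41% to 87% of trials over base rates from 10% down to 2%. Identical arms at about 2% to 5% would leave differences of roughly 4 to 6 points either way unexcluded. The point must be fixed before analysis, since safety is half of the main objective.

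**What to change.** **Section 4.** Replace the equality hypothesis with an estimation aim, for example: *to estimate the difference in complications between axillary and cephalic access*.

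**Section 9.** Add that the risk difference, axillary minus cephalic, will be reported by intention to treat with a two-sided 95% confidence interval (Newcombe or Miettinen-Nurminen) for (a) any peri-procedural complication and (b) electrode problems at follow-up. For (b), name in advance the planned visit used and report how many patients were followed to it, because section 7 ends follow-up when the study ends. A time-to-event estimate would be a reasonable alternative. Add: *a non-significant p-value will not be reported as equal safety*.

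**If the sponsor prefers a non-inferiority claim.** Pre-specify and justify a margin, judge the confidence interval against it, and compute power for that interval method. The trial is open, and the investigators who implant also collect the data, so the margin should be fixed and dated before safety data are reviewed by arm. Add an as-treated or per-protocol analysis: section 2 puts cephalic effectiveness below 85%, and crossover can draw the intention-to-treat arms together and favour a non-inferiority conclusion.

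**Cost.** The estimation route needs edits to two sections and two intervals from data already planned, with no new patients. Its price is a weaker safety claim. Non-inferiority with a margin tighter than those in the working would need more patients.

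### No primary endpoint is named, so axillary superiority could rest on any of three secondary outcomes at p<0.05, and the 80% power belongs to no outcome

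*Combined protocol and SAP*

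**What the plan says.** Section 4 sets two hypotheses: "The axillary venous access pathway is superior in terms of efficacy to the cephalic access" and "The axillary venous access pathway is equal in terms of safety to the cephalic access". Section 5 gives one main objective: "To compare the efficacy and safety of fluoroscopy-guided axillary venous access to improved cephalic venous access in the cardiac stimulation device implant". None of these names a variable, a time point or an effect measure.

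The measurable outcomes first appear in section 6, under secondary objectives. Three concern efficacy: "To compare the success rate of the accesses", then the duration of access, then the duration of the implant. They return in section 7 (Variables) within an unranked list of eight efficacy variables.

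The sample-size text in section 7 gives 240 patients, 80% power, alpha 0.05 and an unquantified allowance for losses. It gives no outcome, expected rates, difference, standard deviation or sidedness. Section 9 specifies an intention-to-treat comparison using t, Mann-Whitney and chi-square tests, all judged at p<0.05, with no hierarchy or multiplicity adjustment.

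**The concern.** The trial makes a directional superiority claim, but nothing says which result would establish it. If any of three tests may do so, 0.05 is not the error rate of that claim.

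A split result is a real possibility. Section 2 describes two randomised comparisons of axillary with cephalic access. The fluoroscopy-guided one "found no difference in success or complications with both techniques, although it was objective a shorter time to get venous access by axillary", with the procedure "performed by physicians without any training in the technique". The venography-guided one was concordant on the outcomes reported: "It found a higher percentage of success and shorter duration of the procedure by the axillary pathway". Neither matches this trial, which uses fluoroscopy and where, according to section 10, "The operators that will perform the study are perfectly trained in the realization of both techniques". If success and duration disagree here, the plan cannot say whether its own hypothesis was met.

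The trial is open, and under section 8 the two investigators recruit, implant and collect the data, with the principal investigator in charge of the analysis. A fixed endpoint is therefore the main protection against choosing one after the results are known.

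**Working it through.** **1. Can 240 be reproduced?** Not from the documents, because outcome, effect, sidedness and loss are all missing. Trying assumed success rates with the pooled two-proportion formula (80% power, alpha 0.05, no continuity correction), and dividing by 1 − loss, several unrelated designs land near 240:

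- 80% v 93%, two-sided: 108 per arm; 108/0.90 = 120; total 240 (10% loss).
- 75% v 90%, two-sided: 100 per arm; 100/0.85 → 118; total 236 (15% loss).
- 85% v 96%, two-sided: 111 per arm; 111/0.95 → 117; total 234 (5% loss).
- 85% v 95%, one-sided: 111 per arm; total 234 (5% loss).

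For a duration, 80% power needs a standardised difference of (1.960 + 0.842) × √(2/120) = 0.36 with no loss. So the figure 240 does not identify a design.

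**2. Chance of a false superiority claim.** Take three tests (the three efficacy-type secondary objectives), no true difference, and normal test statistics with a common correlation ρ. Sidedness and ρ are assumptions. With critical value c, the chance that at least one test favours axillary access significantly is

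1 − ∫ Φ[(c − √ρ·u)/√(1 − ρ)]³ φ(u) du.

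At ρ = 0 with two-sided tests (0.025 in the axillary direction) this is 1 − 0.975³ = 0.073.

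| ρ | Favouring axillary, two-sided 0.05 (one test: 2.5%) | Favouring axillary, one-sided 0.05 (one test: 5%) | Either direction, two-sided (one test: 5%) |
|---|---|---|---|
| 0 | 7.3% | 14.3% | 14.3% |
| 0.5 | 6.3% | 11.8% | 12.5% |
| 0.7 | 5.5% | 10.3% | 10.9% |
| 0.9 | 4.2% | 8.0% | 8.4% |

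Access is a step within the implant, so the two durations should be strongly correlated. With 0.9 between them and 0.5 between each and success, simulation gives 5.4% favouring axillary (two-sided). Whatever the correlations, the two-sided directional figure cannot exceed 3 × 2.5% = 7.5%.

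**3. Power if access success were the endpoint.** With 1:1 allocation, n = 120 per arm. For success rates p₁ and p₂ with mean p̄, two-sided alpha 0.05,

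power = Φ{[|p₂ − p₁|√n − 1.96√(2p̄(1 − p̄))] / √(p₁(1 − p₁) + p₂(1 − p₂))}.

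For cephalic 85% v axillary 95%: (0.10 × √120 − 1.96 × 0.4243)/0.4183 = (1.0954 − 0.8316)/0.4183 = 0.631, and Φ(0.631) = 0.736.

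| Cephalic success (assumed) | v 95%, 120 per arm | v 95%, 108 per arm (10% loss) | v 92%, 120 per arm | v 98%, 120 per arm |
|---|---|---|---|---|
| 80% | 94% | 92% | 77% | 99.5% |
| 85% | 74% | 69% | 40% | 96% |
| 88% | 49% | 45% | 18% | 86% |
| 90% | 31% | 29% | 8% | 74.5% |

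Exact power of the uncorrected chi-square test is slightly higher: 96%, 76%, 52% and 33% down the 95% column at 120 per arm. The only rate in the documents is the remark in section 2 that cephalic effectiveness is below 85%. It describes the technique in general and is not linked to the sample size. Higher cephalic rates are included because this trial uses an improved technique with trained operators.

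**The case against.** The omission itself is not disputable; the arguments against concern its size and its remedy.

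- **Sidedness.** The chi-square test is ordinarily non-directional and the plan never mentions one-sided testing. This stands: the two-sided column is the relevant one, and the conclusion does not need the other.
- **Size of the inflation.** Under the most structured assumption the error is 5.4%, and at correlation 0.9 throughout it is 4.2%. That is modest in absolute terms, and the correlations are assumed. Fair, but 4.2% is still about 1.7 times the 2.5% of a single test, and error inflation is only part of the harm: a split result has no prespecified reading at any correlation.
- **The count of three.** The plan states no rule that any one significant result suffices, and eight efficacy variables are listed. Three matches the secondary objectives and is the restrained count; the plan's silence permits the rule.
- **Power rates.** No axillary rate is given, and low power arises mainly when cephalic success exceeds the 85% background remark. At cephalic 80–85% v 95%, power is 74–94%. Loss to follow-up should also barely affect an outcome recorded at the implant. Both points are right, so the power table is illustrative only.
- **Success listed first.** It could be read as implicitly primary, but list order is not a designation, and the list is headed as secondary.
- **Safety.** The main objective also covers safety, where the hypothesis of equality has no margin. That is a separate gap, which naming an efficacy endpoint does not close.

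**Conclusion.** The concern holds and should be fixed before the results are interpreted. The plan names no outcome that decides its superiority hypothesis, and nothing elsewhere in the protocol supplies one. Followed as written, it allows an axillary claim on any of three tests. The false-claim rate is then 4.2% to 7.3% rather than 2.5%, assuming two-sided tests and common correlations from 0.9 down to 0. The stated 80% power cannot be attached to any test. For access success alone, 240 patients could give anything from 8% to 99.5% over the assumed rates in the table. This shows that the power is unverifiable, not that 240 is wrong.

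**What to change.** - **Section 5:** name one primary efficacy endpoint that alone decides the superiority hypothesis, with its alpha and sidedness. Success of the assigned access, per patient and by intention to treat, is a reasonable candidate because it heads both lists. The sponsor may choose another, provided it is fixed before comparative data are seen.
- **Section 9:** make the other efficacy variables secondary. Either test them in a fixed order only after the primary is significant, or report them with 95% confidence intervals and no superiority claim.
- **Section 7:** state the outcome, rates and loss figure behind 240. If there were none, give the power of 240 for the chosen endpoint over a range of rates and losses (for success, including cephalic rates above 85%). Say that this power does not cover the safety hypothesis.
- **Amendment:** section 7 starts recruitment in September 2017 and section 8 in the fourth quarter of 2017. Both precede the October 2018 version. Make the change by a dated amendment stating whether comparative outcome data had been seen. The operators see each procedure's outcome in this open trial, so the statement should be explicit about what was known.

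The cost is wording in three sections plus the amendment; the change itself adds no patients. There are real downsides. If success is chosen, a win on duration alone no longer supports superiority. The stated power may look less favourable (31–49% if cephalic success is 88–90% v 95%, although 74–94% at 80–85%), and the sponsor would have to accept that or enlarge the trial. If comparative data had been seen, the claim of prespecification is weaker and the amendment must say so.
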